#### 9.4.3.6. Follow-up of Adverse Event

##### Investigator Follow-Up

During the Study Period, the Investigator should follow each AE until the event has resolved to baseline grade or better, the event is assessed as stable, the subject is lost to follow-up, or the subject withdraws consent. Every effort should be made to follow all SAEs considered to be related to Study Drug or related to study procedures until a final outcome can be reported.

Resolution of AE (with dates) should be documented on the AE eCRF and in the subject's medical record to facilitate source data verification.

Investigator should follow-up or support the Sponsor's effort to follow up with all pregnancies reported during the study from either the study subject or the female partner of male study subject until pregnancy outcome is available.

### **Sponsor Follow-Up**

For SAEs, AESI and pregnancy cases in subjects who has completed or terminated study, the Sponsor or a designee should follow-up by telephone, fax, email, and/or a monitoring visit to obtain additional case details and outcome information (e.g., from hospital discharge summaries, consultant reports, autopsy reports) in order to perform an independent medical assessment of the reported case.

## **9.5. Procedures for Handling Special Situations**

### **9.5.1. Abnormalities of Laboratory Tests**

Clinically significant abnormal laboratory test results may, in the opinion of the Investigator, constitute or be associated with an AE. Examples of these include abnormal laboratory results that are associated with symptoms, or require treatment, e.g., bleeding due to thrombocytopenia, tetany due to hypocalcemia, or cardiac arrhythmias due to hyperkalemia. Whenever possible, the underlying diagnosis should be listed as AEs rather than as abnormal laboratory values.

Clinically significant abnormalities will be monitored by the Investigator until the parameter returns to its baseline value or until agreement is reached between the Investigator and Sponsor Medical Monitor. Laboratory abnormalities deemed not clinically significant by the Investigator should not be reported as AEs. Similarly, laboratory abnormalities reported as AEs by the Investigator should be deemed CS on the laboratory sheet.

The Investigator is responsible for reviewing and signing all laboratory reports. The signed clinical laboratory reports will serve as source documents and should include the Investigator's assessment of clinical significance of out of range/abnormal laboratory values.

### **9.5.2. Prescheduled or Elective Procedures or Routinely Scheduled Treatments**

A prescheduled or elective procedure or a routinely scheduled treatment will not be considered an SAE, even if the subject is hospitalized; the Study Center must document all of the following:

- The prescheduled or elective procedure or routinely scheduled treatment was scheduled (or was on a waiting list to be scheduled) prior to obtaining the subject's consent to participate in the study
- The condition that required the prescheduled or elective procedure or routinely scheduled treatment was present before and did not worsen or progress in the opinion of the Investigator between the subject's consent to participate in the study and the timing of the procedure or treatment
- The prescheduled or elective procedure or routinely scheduled treatment is the sole reason for the intervention or hospital admission

### 9.5.3. Dosing Errors

Study Drug (ISIS 757456 or placebo) errors (including overdose, underdose, and administration error) should be documented as Protocol Deviations. A brief description should be provided in the deviation, including whether the subject was symptomatic (list symptoms) or asymptomatic, and the event accidental or intentional.

Dosing details should be captured on the Dosing Case Report Form. If the subject takes a dose of Study Drug (ISIS 757456 or placebo) that exceeds protocol specifications and the subject is symptomatic, then the symptom(s) should be documented as an AE and be reported per Section 9.4.

An overdose is the accidental or intentional use of a drug in an amount higher than the dose being studied. An overdose or incorrect administration of study treatment is not itself an AE, but it may result in an AE. All AEs associated with an overdose or incorrect administration of Study Drug should be recorded on the AE eCRF. If the associated AE fulfills seriousness criteria, the event should be reported to the Sponsor immediately (i.e., no more than 24 hours after learning of the event).

**Should an overdose occur**, the Investigator or designee should refer to the Guidance to Investigator's section of the Investigator's Brochure and contact the Sponsor or designee within 24 hours.

### 9.5.4. Contraception and Pregnancy

Male subjects must continue to use appropriate contraception with their partners, or refrain from sexual activity, as described in Section 6.3.1.

If a male subject makes or believes that he has made someone pregnant during the study, then the Study Center staff must be informed immediately. An Initial Pregnancy Form should be submitted to the Sponsor or designee **within 24 hours** of first learning of the occurrence of pregnancy. Follow-up information including delivery or termination is reported by designating as 'Follow-up' on the Pregnancy Forms and reported within 24 hours.

Payment for all aspects of obstetrical care, child or related care will be the subject's responsibility.

Male subjects: The progress of the pregnancy of a male subject's partner should be followed until the outcome of the pregnancy is known (i.e., delivery, elective termination, or spontaneous abortion). If the pregnancy results in the birth of a child, **the Study Center and Sponsor may follow-up with the mother and may request access to the mother and infant's medical records** to obtain additional information relevant to the pregnancy progress and outcome. A longer follow-up may be required if a newborn child experiences a medical condition. Follow-up will be performed to the extent permitted by the applicable regulations and privacy considerations; e.g., partner ICF may be required.

## 10. STATISTICAL CONSIDERATIONS

### 10.1. Stratification, Subsets, and Covariates

Subjects will be stratified based on either low Screening ACE/ARB dose or high Screening ACE/ARB dose. The **total** dose of the ACE or ARB taken per day is to be calculated based off their stable regimen of antihypertensive medications at Screening. Please refer to [Appendix E](#) for stratification criteria.

### 10.3. Populations

Full Analysis Set (FAS): All randomized subjects who have received at least 1 injection of Study Drug (ISIS 757456 or placebo) and who have at least 1 post-Baseline efficacy or exploratory measurements.

Per Protocol Set: All FAS subjects who received at least 7 of the 9 doses of Study Drug, did not alter Screening antihypertensive medications during the Treatment Period and prior to Study Day 57, and have no significant protocol deviations that would be expected to affect efficacy or exploratory assessments.

Safety Set: All subjects who are randomized and receive at least 1 dose of Study Drug.

PK Set: All subjects who are randomized and receive at least 1 dose of Study Drug and have at least 1 evaluable PK sample.

### 10.4. Definition of Baseline

The baseline for plasma AGT will be define as the average of all values prior to the first dose of Study Drug. The baseline for all other assessments will be defined as the last non-missing measurement prior to the first dose.

### 10.5. Interim Analysis

An interim analysis may be conducted after at least 50% of the subjects have been enrolled.

### 10.6. Planned Methods of Analysis

All case report form (CRF) data, lab data transfers, and any outcomes derived from the data may be provided in the subject data listings. Subject data listings will be presented for all subjects randomized in the study. Descriptive summary statistics including n, mean, median, standard deviation, standard error, interquartile range (25th percentile, 75th percentile), and range (minimum, maximum) for continuous variables, and counts and percentages for categorical variables will be used to summarize most data.

### **10.6.1. Demographic and Baseline Characteristics**

Demographic and Baseline characteristics will be summarized using descriptive statistics by treatment group. Subject randomization will be summarized by treatment group. The subject disposition will be summarized. All subjects enrolled will be included in a summary of subject disposition.

### **10.6.2. Safety Analysis**

The safety analysis will be conducted on the Safety Population.

Treatment duration and amount of Study Drug (ISIS 757456 or placebo) received will be summarized by treatment group. Subject incidence rates of all AEs will be tabulated by Medical Dictionary for Regulatory Activities (MedDRA™) system organ class, and by MedDRA™ term. Narratives of treatment emergent deaths, serious and AEs of special interest, including early withdrawals due to AEs, will also be provided.

All treatment emergent AEs, all treatment emergent AEs potentially related to Study Drug, all treatment emergent serious AEs, and all treatment emergent serious AEs potentially related to Study Drug (ISIS 757456 or placebo) will be summarized.

Laboratory tests to ensure subject safety including chemistry panel, complete blood count with differential, coagulation panel, complement etc., will be summarized by study visits for each treatment group. These safety variables will also be presented as change and percent change from Baseline over time after Study Drug (ISIS 757456 or placebo) administration, as appropriate.

Vital sign and ECG measures will be tabulated by treatment group. In addition, the number of subjects who experience abnormalities in clinical laboratory evaluations will be summarized by treatment group.

### **10.6.3. Efficacy Analysis**

The primary analysis will be the comparison of percent change from Baseline to Study Day 57 (Study Week 9) in plasma AGT between ISIS 757456 80 mg group and placebo group in the Per Protocol Set. The data will be analyzed using analysis of variance (ANOVA) with treatment and randomization stratification factor (low ACE/ARB dose regimen vs. high ACE/ARB dose regimen) as independent variables. In the case data departs substantially from normality, the nonparametric van Elteren test will be employed instead.

The secondary efficacy analyses will be performed in a similar way to the primary analysis, which include:

- Comparison of change and percent change from Baseline to each schedule post-Baseline visit in AGT between ISIS 757456 80 mg group and placebo group in Per Protocol Set (PPS) and FAS
- Comparison of change from Baseline to each schedule post-Baseline visit in in-clinic SBP and DBP between ISIS 757456 80 mg group and placebo group in PPS and FAS

#### **10.6.4. Pharmacokinetic Analysis**

Plasma ISIS 757456 concentrations at trough during the Treatment Period and concentrations observed during the Post-Treatment Evaluation Period will be listed by dose, study day, time point, and summarized using descriptive statistics.

Other plasma PK parameters, as appropriate, may be determined or calculated at the discretion of the PK scientist.

Metabolite identification and profiling may be conducted on select plasma samples.

Additional details regarding the PK analysis will be described in the Statistical Analysis Plan (SAP).

Analysis of potential exposure-response relationship between plasma AGT and ISIS 757456 exposure (such as  $C_{trough}$ ) will be conducted. Relationships between other relevant biomarkers and clinical endpoints with PK measures may also be explored, if deemed appropriate.

Population PK and PK/PD analysis may be performed using PK data from this Study, and/or combined with other ISIS 757456 clinical PK/PD data later in the development timeline.

## **11. INVESTIGATOR'S REGULATORY OBLIGATIONS**

### **11.1. Informed Consent**

The written informed consent document should be prepared in the language(s) of the potential patient population, based on an English version provided by the Sponsor.

Before a subject's participation in the trial, the Investigator is responsible for obtaining written informed consent from the subject after adequate explanation of the aims, methods, anticipated benefits, and potential hazards of the study and before any protocol-specific screening

procedures or any Study Drug (ISIS 757456 or placebo) are administered. The subject must be given sufficient time to consider whether to participate in the study.

The acquisition of informed consent and the subject's agreement or refusal to notify his/her primary care physician should be documented in the subject's medical records and the informed consent form should be signed and personally dated by the subject and by the person who conducted the informed consent discussion (not necessarily an Investigator). The original signed informed consent form should be retained in the Study Master File and in any other locations required by institutional policy, and a copy of the signed consent form should be provided to the subject.

## **11.2. Ethical Conduct of the Study**

All applicable regulations and guidelines of current GCP as well as the demands of national drug and data protection laws and other applicable regulatory requirements must be followed.

## **11.3. Institutional Review Board**

A copy of the protocol, proposed informed consent form, other written subject information, and any proposed advertising material must be submitted to the IRB for written approval. A copy of the written approval of the protocol and informed consent form must be received by the Sponsor before recruitment of subjects into the study and shipment of Study Drug. A copy of the written approval of any other items/materials that must be approved by the Study Center or IRB must also be received by the Sponsor before recruitment of subjects into the study and shipment of Study Drug. The Investigator's Brochure must be submitted to the IRB for acknowledgement.

The Investigator must submit to and, where necessary, obtain approval from the IRB, for all subsequent protocol amendments and changes to the informed consent document. The Investigator should notify the IRB of deviations from the protocol in accordance with ICH GCP. The Investigator should also notify the IRB of SAEs occurring at the Study Center and other AE reports received from the Sponsor, in accordance with local procedures.

The Investigator will be responsible for obtaining annual IRB approval/renewal throughout the duration of the study. Copies of the Investigator's reports, all IRB submissions and the IRB continuance of approval must be sent to the Sponsor.

## **11.4. Subject Confidentiality**

The Investigator must ensure that the subject's confidentiality is maintained. On the case report forms or other documents submitted to the Sponsor, subjects should be identified by initials (if permitted by local law) and a subject identification number only. Documents that are not for submission to the Sponsor (e.g., signed informed consent forms) should be kept in strict confidence by the Investigator.

In compliance with Federal and local regulations/ICH GCP Guidelines, it is required that the Investigator and institution permit authorized representatives of the company, of the regulatory agency(s), and the IRB direct access to review the subject's original medical records for verification of study-related procedures and data. Direct access includes examining, analyzing, verifying, and reproducing any records and reports that are important to the evaluation of the

study. The Investigator is obligated to inform and obtain the consent of the subject to permit named representatives to have access to his/her study-related records without violating the confidentiality of the subject.

## **12. ADMINISTRATIVE AND LEGAL OBLIGATIONS**

### **12.1. Protocol Amendments**

Protocol amendments must be made only with the prior approval of the Sponsor. Agreement from the Investigator must be obtained for all protocol amendments and amendments to the informed consent document. The regulatory authority and IRB must be informed of all amendments and give approval for any amendments likely to affect the safety of the subjects or the conduct of the trial. The Investigator **must** send a copy of the approval letter from the IRB to the Sponsor.

### **12.2. Study Termination**

The Sponsor reserves the right to terminate the study. The Investigator reserves the right to terminate their participation in the study, according to the terms of the site contract. The Investigator should notify the IRB in writing of the trial's completion or early termination and send a copy of the notification to the Sponsor or designee.

### **12.3. Study Documentation and Storage**

An eCRF utilizing an Electronic Data Capture (EDC) application will be used for this study.

The Investigator should ensure that all appropriately qualified persons to whom he/she has delegated trial duties are recorded on a Sponsor-approved Delegation of Site Responsibilities Form.

Source documents are original documents, data, and records from which the subject's case report form data are obtained. These include but are not limited to hospital records, clinical and office charts, laboratory and pharmacy records, imaging, and correspondence. In this study, eCRF may not be used as source documents.

The Investigator and Study Center staff are responsible for maintaining a comprehensive and centralized filing system of all study-related (essential) documentation in accordance with ICH GCP, suitable for inspection at any time by representatives from the Sponsor and/or applicable regulatory authorities. Elements should include:

- Subject files containing completed case report forms, informed consents, and supporting copies of source documentation
- Study files containing the protocol with all amendments, Investigator's Brochure, copies of pre-study documentation and all correspondence to and from the IRB and the Sponsor.

- If drug supplies are maintained at the Study Center, proof of receipt, Study Drug Product Accountability Record, Return of Study Drug Product for Destruction, final Study Drug product reconciliation, and all drug-related correspondence

In addition, all original source documents supporting entries in the case report forms must be maintained and be readily available.

No study document should be destroyed without prior written agreement between the Sponsor and the Investigator. Should the Investigator wish to assign the study records to another party or move them to another location, he/she must notify the Sponsor.

#### **12.4. Study Monitoring**

The Sponsor representative and regulatory authority inspectors are responsible for contacting and visiting the Investigator for the purpose of inspecting the facilities and, upon request, inspecting the various records of the trial (e.g., case report forms and other pertinent data) provided that subject confidentiality is respected.

The Sponsor monitor is responsible for inspecting the case report forms at regular intervals throughout the study to verify adherence to the protocol; completeness, accuracy, and consistency of the data; and adherence to local regulations on the conduct of clinical research. The monitor should have access to subject medical records and other study-related records needed to verify the entries on the case report forms.

The Investigator agrees to cooperate with the monitor to ensure that any problems detected in the course of these monitoring visits, including delays in completing case report forms, are resolved.

In accordance with ICH GCP and the Sponsor's audit plans, this study may be selected for audit by representatives from the Sponsor's Clinical Quality Assurance Department. Inspection of Study Center facilities (e.g., pharmacy, drug storage areas, laboratories) and review of study-related records will occur to evaluate the trial conduct and compliance with the protocol, ICH GCP, and applicable regulatory requirements.

To ensure the quality of clinical data a clinical data management review will be performed on subject data received by the Sponsor. During this review, subject data will be checked for consistency, omissions, and any apparent discrepancies. In addition, the data will be reviewed for adherence to the protocol and GCP. To resolve any questions arising from the clinical data management review process, data queries and/or Study Center notifications will be sent to the Study Center for completion and return to Sponsor.

The Principal Investigator will sign and date the indicated places on the case report form. These signatures will indicate that the Principal Investigator inspected or reviewed the data on the case report form, the data queries, and the Study Center notifications, and agrees with the content.

#### **12.5. Language**

Case report forms must be completed in English. Generic names and trade names are acceptable for concomitant medications. Combination medications should be recorded using their trade name.

All written information and other material to be used by subjects and investigative staff must use vocabulary and language that are clearly understood.

## **12.6. Compensation for Injury**

The Sponsor maintains appropriate insurance coverage for clinical trials and will follow applicable local compensation laws. Subjects will be treated and/or compensated for any study-related illness/injury in accordance with the information provided in the Compensation for Injury section of the Informed Consent document.

**14. APPENDICES**

.

**APPENDIX A. SCHEDULE OF PROCEDURES**

**Appendix A Schedule of Procedures**

	Screen	Treatment Period (8 Weeks)									Post-Treatment Period (13 Weeks)					
Study Week		Wk1	Wk2	Wk3	Wk4	Wk5	Wk6	Wk7	Wk8	Wk9	Wk10	Wk12	Wk14	Wk18	Wk21	
Study Day	D-28 to D-1	D1	D3	D8	D15	D22	D29	D36	D43	D50	Treatment Early Term  / D57	D64	D78	D92	D120	PT Early Term  / D141
Visit Window (Days)	NA	NA	+2	± 2	± 2	± 2	± 2	± 2	± 2	± 2	± 2	± 2	± 2	± 5	± 5	± 5
Scheduled Visit #	1	2	3	4	5	6	7	8	9	10	11	12	13	14	15	16
Informed Consent	X															
Inclusion/Exclusion	X	X a														
Medical History	X															
Low Sodium Diet Education	X	← Continuous Counseling & Monitoring →														
CVD Risk Factors	X															
Body Weight and Height 	X	X									X					X
Physical Exam 	X	X									X					X
ECG (12-Lead)	X										X					
Vital Signs (clinic) 	X	X a	X a	X a	X a	X a	X a	X a	X a	X a	X	X	X	X	X	X
HIV, Hep B & C	X															
FSH 	X															
Pregnancy Test 	X															
Chemistry Panel (Fasting) 	X	X a		X a	X a	X a	X a	X a	X a	X a	X	X	X	X	X	X
Renal Urine Biomarkers and Archived Urine Sample 	X	X a		X a	X a	X a	X a	X a	X a	X a	X	X	X	X	X	X
TSH, FT3, FT4	X															
Hematology 	X	X a		X a	X a	X a	X a	X a	X a	X a	X	X	X	X	X	X
Urinalysis 	X	X a		X a	X a	X a	X a	X a	X a	X a	X	X	X	X	X	X
Plasma AGT	X	X a	X a	X a	X a	X a	X a	X a	X a	X a	X	X	X	X	X	X
Exploratory	X	X a				X a					X		X	X	X	X
hsCRP		X a									X					X
PT, INR, aPTT	X															
Study Drug Administration		X	X	X	X	X	X	X	X	X						

**Appendix A Schedule of Procedures (Continued)**

	Screen	Treatment Period (8 Weeks)									Post-Treatment Period (13 Weeks)					
Study Week		Wk1	Wk2	Wk3	Wk4	Wk5	Wk6	Wk7	Wk8	Wk9	Wk10	Wk12	Wk14	Wk18	Wk21	
Study Day	D-28 to D-1	D1	D3	D8	D15	D22	D29	D36	D43	D50	Treatment Early Term  / D57	D64	D78	D92	D120	PT Early Term  / D141
Visit Window (Days)	NA	NA	+2	± 2	± 2	± 2	± 2	± 2	± 2	± 2	± 2	± 2	± 2	± 5	± 5	± 5
Scheduled Visit #	1	2	3	4	5	6	7	8	9	10	11	12	13	14	15	16
AEs	X	X	X	X	X	X	X	X	X	X	X	X	X	X	X	X
Concomitant Medications	X	X	X	X	X	X	X	X	X	X	X	X	X	X	X	X
PK Blood Sampling 		X a	X a	X a	X a	X a	X a	X a	X a	X a	X	X	X	X	X	X
Immunogenicity Testing		X a									X					X
Archived Serum Sample 		X		X			X			X	X			X		X

Note: D = Day  
W = Week

- 1 Full physical exam to be given at Screening and abbreviated physical exam to be given during Treatment and Post-Treatment Period as indicated to assess changes from Screening
- 2 Vital Signs (clinic): Blood Pressure (SBP/DPB; sitting), Orthostatic assessment (supine and standing, required at Screening), HR, RR, T. Vital sign assessments will be reviewed by the study doctor at each visit prior to dosing.
- 3 Women who are not surgically sterile, as confirmation of menopause
- 4 Women who are not surgically sterile. Serum test to be done
- 5 Refer to [Appendix C](#) for PK sampling schedule
- 6 Stored at -80 °C for follow-up exploration of laboratory findings and/or AEs (e.g., measurement of cytokine and/or chemokine levels, measurement of additional markers of kidney function, measurement of antibodies, etc.) in this or subsequent clinical studies of ISIS 757456
- 7 If the platelet value, serum creatinine or liver enzyme tests are uninterpretable (e.g., due to clumping, hemolysis or quantity not sufficient) a repeat blood specimen; should be re-drawn as soon as possible (ideally within 7 days) and not meet a stopping rule prior to next dose. Due to time constraints, a local lab draw is recommended if a repeat blood specimen is necessary to continue dosing at any time after Study Day 1 to Study Day 8.
- 8 Height at Screening only
- 9 Subjects who terminate treatment or post-treatment early from the study should be encouraged to participate in an early termination visit, at which time the Study D57 or Study D141 assessments should be conducted, respectively
- 10 Fasting is not required at Screening visit. Fasted samples should be taken after fasting for at least 8 hours. During this time the subject can drink water and they should ensure that they consume sufficient water in order to not become dehydrated.

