### 5.1. Inclusion Criteria

1. Must have given written informed consent (signed and dated) and any authorizations required by local law and be able to comply with all study requirements
2. Males or females aged 18–75 inclusive and weighing  $\geq 50$  kg at the time of informed consent
3. Satisfy the following:
  - a. Females: must be non-pregnant and non-lactating, and either:
    - i. surgically sterile (e.g., tubal occlusion, hysterectomy, bilateral salpingectomy, bilateral oophorectomy) or,
    - ii. post-menopausal (defined as 12 months of spontaneous amenorrhea in females  $> 55$  years of age or, in females  $\leq 55$  years, 12 months of spontaneous amenorrhea without an alternative medical cause and follicle stimulating hormone (FSH) levels in the postmenopausal range for the laboratory involved)
  - b. Males: Surgically sterile (i.e., bilateral orchidectomy) or abstinent\*, if engaged in sexual relations with a woman of child-bearing potential (WOCBP), the subject or subject's non-pregnant female partner must be using a highly effective contraceptive method from the time of signing the informed consent form until at least 13 weeks after the last dose of Study Drug (ISIS 757456 or placebo)

\* True abstinence (i.e., refraining from heterosexual intercourse throughout the duration of study participation) is only acceptable. Periodic abstinence (e.g., calendar, ovulation, symptothermal, post-ovulation methods), declaration of abstinence for the duration of a trial and withdrawal are not acceptable methods of contraception

4.  $BMI \leq 35.0 \text{ kg/m}^2$
5. Brachial circumference  $\geq 22$  and  $\leq 37$  cm (8.7 and 14.6 inches)
6. Subject must have been diagnosed with essential HTN for a minimum of 3 months prior to screening
7. At Screening, the subject must have a plasma AGT concentration  $\geq 20 \text{ } \mu\text{g/mL}$ . Up to 1 additional repeat test may be allowed in order to qualify with consultation of the Sponsor Medical Monitor
8. At Screening, the subject must have been on a stable regimen of 2 to 3 antihypertensive medications for at least 1 month prior to screening and will be required to maintain this regimen throughout the Study, using either an angiotensin-converting enzyme inhibitor (ACEi) or an angiotensin II receptor blocker (ARB), as well as 1 or 2 additional antihypertensive medications in the following categories:
  - a. beta blocker
    - i. acebutolol
    - ii. atenolol
    - iii. betaxolol
    - iv. bisoprolol

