## **6.3. Restriction on the Lifestyle of Subjects**

### **6.3.1. Contraception Requirements**

All male subjects must refrain from sperm donation and either be abstinent† or use highly effective contraception from the time of signing the informed consent form until at least 13 weeks after their last dose of study treatment.

For male subjects engaged in sexual relations with a WOCBP either the subject or their female partner must use highly effective contraception from the time of signing the informed consent until 13 weeks after the subject's last dose of study treatment.

For the purposes of this study, WOCBP are defined as any female who has experienced menarche, and who does not meet 1 of the following conditions:

- Postmenopausal: 12 months of spontaneous amenorrhea in females > 55 years of age or, in females ≤ 55 years, 12 months of spontaneous amenorrhea without an alternative medical cause and FSH levels in the postmenopausal range for the laboratory involved
- 6 weeks after surgical bilateral oophorectomy with or without hysterectomy
- Post-hysterectomy

For the purposes of the study, highly effective contraception is defined as follows:

For male subjects:

- Highly effective male contraception includes a vasectomy with negative semen analysis at follow-up, or the non-pregnant female partner of WOCBP uses a highly effective contraceptive method (defined below)
- Male subjects with partners that are pregnant must use condoms as contraception to ensure that the fetus is not exposed to the Study Drug

For female partners of male subjects, highly effective female contraception methods comprise:

- Surgical sterilization (e.g., bilateral tubal occlusion), hormonal contraception associated with inhibition of ovulation (combined estrogen and progestogen containing, or progestogen-only), intrauterine contraception device or intrauterine hormone-releasing system

[figure not shown]
†**Note:** Only true abstinence (i.e., refraining from heterosexual intercourse throughout the duration of study participation) is acceptable. Periodic abstinence (e.g., calendar, ovulation, symptothermal, post-ovulation methods), declaration of abstinence for the duration of a trial and withdrawal are not acceptable methods of contraception.

Note: A female condom and a male condom should not be used together as friction between the 2 can result in either or both products failing.

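### No pregnancy test is scheduled for a pre-menopausal woman admitted on a tubal procedure alone, although the protocol's only definition of child-bearing potential includes her

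*Combined protocol and SAP*

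**What the plan says.** Five places in the protocol bear on this.

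- **Section 5.1, item 3a.** "Females: must be non-pregnant and non-lactating, and either" surgically sterile or post-menopausal. The first route reads: "surgically sterile (e.g., tubal occlusion, hysterectomy, bilateral salpingectomy, bilateral oophorectomy) or". Tubal procedures therefore count as sterility for eligibility.
- **Section 6.3.1.** "WOCBP are defined as any female who has experienced menarche, and who does not meet 1 of the following conditions". The three conditions are menopause, "6 weeks after surgical bilateral oophorectomy with or without hysterectomy", and hysterectomy. Tubal occlusion and salpingectomy are not among them. Bilateral tubal occlusion appears later in the section, as an example of highly effective contraception for female partners of male subjects.
- **Appendix A.** The pregnancy test row is marked in the Screening column only. Footnote 4 reads: "Women who are not surgically sterile. Serum test to be done". Footnote 3 restricts FSH testing to the same women.
- **Appendix B.** Serum beta-hCG is listed among the screening tests for women where applicable, with no further rule.
- **Sections 9.4.3.6 and 9.5.4.** The follow-up section expects "pregnancies reported during the study from either the study subject or the female partner of male study subject until pregnancy outcome is available". The pregnancy section opens its notification step with: "If a male subject makes or believes that he has made someone pregnant during the study, then the Study Center staff must be informed immediately".

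**The concern.** Item 3a makes absence of pregnancy a condition of entry for every female, whichever route she enters by. One would expect the scheduled test to cover at least those enrolled women whom the protocol regards as able to conceive. Instead, footnote 4 uses the eligibility vocabulary (surgically sterile or not), while Section 6.3.1 sets child-bearing potential by a narrower list of surgery. Women with only a tubal procedure fall between the two.

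At stake is whether a stated entry criterion has a scheduled check in that group before dosing with an investigational drug. The protocol treats fetal exposure as something to control: Section 6.3.1 requires condoms for men whose partners are pregnant, and contraception until 13 weeks after the last dose. If a female subject did become pregnant, a site reading Section 9.5.4 would find a notification step addressed to male subjects only.

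**Working it through.** No arithmetic applies, and the plan states no figure to reproduce. The check sorts eligible females under item 3a by their status in Section 6.3.1 and by footnote 4.

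1. **Post-menopausal, no sterilising surgery.** Eligible. Not of child-bearing potential. Test scheduled at Screening.
2. **Hysterectomy, or bilateral oophorectomy at least 6 weeks earlier.** Eligible as surgically sterile. Not of child-bearing potential. No test scheduled.
3. **Tubal occlusion or bilateral salpingectomy, and post-menopausal.** Eligible. Not of child-bearing potential. No test scheduled.
4. **Tubal occlusion or bilateral salpingectomy only, pre-menopausal.** Eligible as surgically sterile. Meets none of the three exempting conditions, so of child-bearing potential as Section 6.3.1 is worded. No test scheduled.

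The surgical examples in item 3a are tubal occlusion, hysterectomy, bilateral salpingectomy and bilateral oophorectomy. Removing the two that Section 6.3.1 exempts (hysterectomy and oophorectomy) leaves tubal occlusion and bilateral salpingectomy. Group 4 is where the passages conflict.

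Two details follow.

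- **Size of the gap.** No female subject has a test scheduled after Screening, so group 4 differs from group 1 by one test: 0 against 1.
- **Telling group 3 from group 4.** At age 55 or under, Section 6.3.1 needs an FSH level in the post-menopausal range as well as 12 months of amenorrhea. Footnote 3 schedules no FSH for a surgically sterile woman, so the schedule does not supply that result for her.

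On notification, Section 9.4.3.6 and the sponsor follow-up paragraph after it both contemplate pregnancy in a study subject. In Section 9.5.4 the trigger names a male subject, the initial form and its 24-hour limit follow in that same paragraph, and the later follow-up text is headed for male subjects. No passage gives a form or time limit expressly for a female subject's own pregnancy.

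**The case against.** The best reply is that the conflict comes from applying a partner definition to subjects. In Section 6.3.1 every duty falls on male subjects, and in Section 5.1 the term for child-bearing potential appears only in item 3b, about their partners. Female eligibility and footnotes 3 and 4 share one vocabulary and agree with each other. There is also a sensible reason to test the post-menopausal group: their status rests on amenorrhea, so FSH and hCG are paired. And Section 6.3.1 itself classes tubal occlusion as highly effective contraception, so the risk in group 4 is low on the protocol's own terms.

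Much of that stands. It does not dispose of the point, because the definition is worded for any female for the purposes of the study and no other is given. Footnote 4 does not define surgical sterility, so the list in item 3a is the only meaning available for female subjects.

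A reader might infer more than the documents support:

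- **That these women can never be tested, or that their eligibility goes unverified.** The documents show only that no test is scheduled. An unscheduled test is not forbidden, Appendix B leaves room for one, and Section 4.2 requires the investigator to verify eligibility before randomisation.
- **That the gap runs through all 16 visits or about 25 weeks.** No female is tested after Screening, so the difference is the single Screening test.
- **That a known number of subjects is exposed.** The documents give neither the share of women nor the share with tubal procedures. With entry allowed up to age 75, many women with a tubal procedure could be post-menopausal and outside the affected group.
- **That pregnancy in a female subject is unprovided for.** Section 9.4.3.6 requires follow-up by investigator and sponsor. A congenital anomaly in the offspring of a male or female subject is a serious adverse event (Section 9.3.3), reportable within 24 hours (Section 9.4.1). What is missing is the notification step for the pregnancy itself.

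**Conclusion.** The point holds as an internal inconsistency with a limited safety consequence. If sites follow footnote 4 as written, the non-pregnant criterion has no scheduled laboratory check in the one eligible group that Section 6.3.1, as worded, counts as of child-bearing potential. The size is one Screening test per affected woman; the number of such women is unknown and may be small or zero. Sample size, type I error and the efficacy analyses are unaffected.

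This rests on two readings: that the Section 6.3.1 definition applies to female subjects as its wording says, and that surgical sterility in footnote 4 means what item 3a says. If the sponsor intended the definition for partners only, the text should say so. That would remove the contradiction without adding a check. Which definition is right is for the sponsor to decide. The change is worth making because it is cheap and concerns an entry criterion.

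**What to change.** Reconcile item 3a (and the same text in the synopsis), Section 6.3.1 and footnote 4 on one definition, and state whether it applies to female subjects, to partners, or to both. Word footnote 4, and the qualifier on the hCG entry in Appendix B, so that the existing Screening serum test covers every enrolled female whom that definition counts as of child-bearing potential, as well as those already tested. If menopausal status decides who is tested, check that footnote 3 provides the FSH result needed to establish it.

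Separately, align Section 9.5.4 with Section 9.4.3.6, so that the pregnancy form and its 24-hour limit expressly apply to a female subject's own pregnancy.

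The cost is amendment wording and, in the women concerned, one added analyte on blood already drawn at Screening. The assay is already listed in Appendix B and no visit is added.
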